4.2 HANDLING MISSING DATA

The frequency (with percentage) of losses to follow-up (defaulters and withdrawals) over the 6 months of the study will be reported by randomised group and compared between the groups.

The availability of the outcome data for the primary outcome will be summarised by randomised group. The generalised linear mixed model implicitly accounts for data missing at random, however the data missing mechanism will be explored. A logistic regression model will explore any association between baseline characteristics and availability of the primary outcome.

Any changes to the assumptions made in the primary analysis i.e. data missing at random, will be considered in a sensitivity analysis.

The impact of any missing primary outcome data on the primary analysis will be assessed by carrying out a sensitivity analyses based on imputing (multiple imputation) the missing values.

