2.1.1 PRIMARY OUTCOME FOR THE PRIMARY OBJECTIVE

The primary outcome is 'living at home' at 6 months.

Living at home is defined as the inverse of death or living in a residential care setting. It is derived from a place of assessment variable, (a 5-category variable, 1 = hospital assessment centre, 2 = in-patient hospital, 3 =

residential care home, 4 = patient's home, and 5 = other) and the patient's death status (0 = alive, 1 = dead) reported at the 6 months visit. Living at home will be coded as a binary variable (1 = alive and living at home, 0 = otherwise (including deaths and living at residential care). Living at home will be computed as 0 if death status = 1 (dead) or place of assessment = 3 (residential care home), or place of assessment = 5 (other) and other = "Nursing Home" (variable *assessoth6m*), otherwise living at home = 1, as long as patient also has a visit date for the particular time point.

Additional information about the residential care (variable *admitryr*) will be used for patients with a place of assessment = 1 (hospital assessment centre) or = 2 (in-patient hospital) to verify where these patients were admitted from. If patients have been in residential care they will be coded as 'not living at home', if patients are not recorded as having been in residential care then they will be assumed to have been admitted from 'home'.

If the patient's death status is missing and the patient's place of assessment has been completed, the patient will be assumed to be alive. In cases where the place of assessment and death status are conflicting (i.e. place of assessment is complete but the patient has been reported as dead) then the patient death form CRF will be used to confirm whether the patient is alive or dead. If the place of assessment and the patient's death status are both missing, then the primary outcome will be missing. This information will be coded as a binary variable (0 = death or not living at home, 1 = alive and living at home) to be used in the analysis.

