the patient death form CRF. If a patient has been reported as dead at 6 or 12 months on the follow-up CRF (variable *deathyn*) it will be checked against the date of death on the Patient Death CRF (variable *deathdat*). If there is conflicting information between the follow-up form and the death form, the death form will overrule the Follow up CRF. If neither the follow-up form nor the death form have been completed then the TM will check with the site if the patient has died.

3) New long-term residential care at 1 month and 6 months

Subsequent admission to residential care is measured at 1 month, and 6 months follow up (variable *admitryn*). This will be coded as a binary variable (0 = No, 1 = Yes). The 6 months admission to residential care data will include the data collected at the 1 month time point.

4) Cognitive impairment at baseline and 6 months (MoCA)

The Montreal Cognitive Assessment (MoCA) [2] is used to derive a variable for cognitive impairment, and is assessed at baseline and 6 months follow-up. The MoCA comprises 8 sections with a total of 30 questions administered by a qualified health professional (variables *mocavis mocanam mocaatt mocalan mocaabs mocarec mocaori*). A total MoCA score will be derived by summing the score from each section of the questionnaire, only patients with complete MoCA will have a total MoCA score computed, an extra point is added to the total score if the patient has 12 or less years of education. The possible range of scores for the MoCA range from 0 to 30, with a score of 26 or above is considered normal. If the patient is visually impaired or if they are frail and unable to write and draw, the visuospatial/executive section (variable *mocavis*) and the naming section (variable *mocanam*) are excluded and is scored out of 22 instead, a score of 18 or above is considered normal. Cognitive impairment will be coded as a binary variable (0 = score less than 26 (less than 18 if visually impaired), 1 = score 26 or more (18 or more if visually impaired)).

5) Activities of daily living at baseline and 6 months (Barthel index)

The Barthel index [3] is used to derive a variable for activities of daily living, and is assessed at baseline and 6 months follow-up. The Barthel index consists of 10 questions (variables *biadl1 – biadl10*), and has a possible range of scores from 0 (completely dependent) to 20 (completely independent). The final Barthel index score is derived by summing the 10 items.

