4.1 PRIMARY OUTCOME

The primary outcome is living at home at 6 months follow-up. A generalised linear mixed model will be fitted to the data with living at home at 6 months as the dependent variable. The model will include intervention arm, gender, and known cognitive decline (IQCODE, the full score will be included in the model) as fixed effects, as well as stratification factors; centre as a random effect. If sites recruited only a small number of patients to the study then these will be grouped together in an 'other' category for the random effect. The

adjusted relative risk between randomised groups with 95% confidence intervals and p-value for living at home at 6 months will be derived from the model.

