6 SENSITIVITY ANALYSIS

Sensitivity analysis will be conducted with respect to the primary outcome only (unless explicitly stated) and will explore the sensitivity of results to different assumptions regarding missing data, outliers and departure from randomisation policy.

- 1) The generalised linear mixed model assumes that the data is missing at random (MAR). A logistic regression analysis will be conducted to investigate factors at baseline (if any) that are predictive of non-response. If any factors are associated with non-response, the generalised linear mixed model in the primary analysis will be re-run with these factors included as fixed covariates in the model.
- 2) Some patients might have missing data for the 'living at home' at 6 months outcome due to missing place of assessment and/or death status. These patients will have their missing place of assessment and/or death status replaced with each of the alternatives for these variables:
 - i) Living at home and alive
 - ii) Not living at home and alive
 - iii) Dead

The 'living at home' at 6 months outcome will be re-derived, and the generalised linear mixed model in the primary analysis in section 4.1 will be re-conducted with each of these replacements to the outcome.

- 3) Some patients might have missing data for the 'living at home' at 6 months outcome due to missing place of assessment and/or death status. Patients with missing 'living at home' at 6 months outcome will have their missing place of assessment and/or missing death status imputed using multiple imputation (MI). A fully inclusive MI will be conducted with; gender, age, education, place of baseline assessment, if consent signed by 'consultee', and other factors expected to relate to the main outcome (i.e. practice, presenting problems at baseline, diagnosis of delirium at baseline) as covariates. The primary outcome will then be re-derived using the same method as in section 2.1.1. The generalised linear mixed model in the primary analysis in section 4.1 will be repeated for the imputed dataset and the results compared to those from the primary analysis.

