Appendix II. Outcome assessment schedule

Outcomes	Visits					
	Baseline	3 days	5 days	1 month	6 months	12 months
Demographics	X					
Medical history	X					
Barthel index of activities of daily living (Barthel)	X				X	
Confusion assessment method (CAM)	X	X	X	X		
Charlson comorbidity index	X				X	
Health resource questionnaire	X				X	
Short form of the informant questionnaire on cognitive decline in the elderly (IQCODE short)	X					
Montreal cognitive assessment (MOCA)	X				X	
EQ-5D-5L (UK English)	X				X	
Adverse event assessments		X	X		X	X
Collection of mortality/living at home	X	X	X	X	X	X

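### The primary model is a complete-case analysis, although the SAP says it accounts for data missing at random, and the multiple imputation meant to check it lists baseline variables only and so cannot detect loss related to early deterioration.

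*SAP*

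**What the plan says.** Section 4.1: "A generalised linear mixed model will be fitted to the data with living at home at 6 months as the dependent variable". On covariates: "The model will include intervention arm, gender, and known cognitive decline (IQCODE, the full score will be included in the model) as fixed effects", with centre as a random effect. There is no patient-level random effect and no earlier outcome in the model.

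Section 2.1.1: "If the place of assessment and the patient's death status are both missing, then the primary outcome will be missing".

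Section 4.2 says of this model: "The generalised linear mixed model implicitly accounts for data missing at random". Section 6 item 1 repeats the assumption.

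Section 6 item 3 describes the imputation: "A fully inclusive MI will be conducted with; gender, age, education, place of baseline assessment", then consultee consent and other factors related to the outcome, which it spells out as "practice, presenting problems at baseline, diagnosis of delirium at baseline". The missing components are imputed and the outcome is re-derived by the rules of section 2.1.1.

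On what is known before 6 months, section 2.1.2 item 3 says: "Subsequent admission to residential care is measured at 1 month, and 6 months follow up". Item 10 of that section gives the same two time points for hospital admission. Appendix II marks the row "Collection of mortality/living at home" at every visit, including 1 month.

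**The concern.** A mixed model uses the data of patients who drop out when it contains their earlier outcomes. The section 4.1 model contains none. A reader of section 4.2 would think that incomplete patients are being used, when they are simply left out.

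The imputation should then be the real check on missing data, but it draws on the same kind of information as the primary model. A patient in residential care at 1 month and then lost is imputed like an otherwise similar patient who was at home at 1 month. If such losses differ between arms, which is possible in an open trial, the two analyses would err together, and their agreement would be reported as reassurance that it cannot give.

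**Working it through.** **Planning figure.** Section 2.3 gives event rates of 50% and 40%, 2:1 allocation, alpha 0.05 (taken as two-sided), power around 83% and 6% attrition. The two-proportion formula with continuity correction gives 329 controls and 658 HAH patients, 987 in total, and 987 / 0.94 = 1050. The stated size is reproduced, and this point does not affect it.

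**What the primary model uses.** There is one row per patient. A patient with a missing response has no likelihood term, so the fit equals that on observed patients only. Fixed arm, gender and IQCODE and random centre make it valid if missingness depends on those alone.

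**What the imputation uses.** Set against section 4.1, the list in section 6 item 3 has gender but not IQCODE or centre. It has practice, which the SAP defines nowhere (section 2.4 stratifies by centre). Nothing on the list is measured after baseline. Randomised arm is not named either. That is a separate matter, not counted in the sizes below, though the fix covers it.

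**Size of the shared bias.** Taken from section 2.3: living at home 50% (control) and 60% (HAH), a difference of 10 points and RR 1.20, with attrition a = 6%. The SAP states the 50% for 12 months; it is used here at 6 months, as the plan does. Assumed, because the SAP gives no figures: a share q not at home at 1 month; 10% of these at home at 6 months (h1); missingness r = 3 times as likely in this group; and 15% attrition as an alternative.

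- At home at 6 months among the rest: h0 = (p − q·h1) / (1 − q)
- Missing among the rest: m0 = a / [(1 − q) + q·r]; in the poor-status group: m1 = r·m0
- Observed proportion: [(1 − q)(1 − m0)h0 + q(1 − m1)h1] / (1 − a)

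Example, control arm, q = 25%, a = 6%: h0 = (0.50 − 0.025) / 0.75 = 0.6333; m0 = 0.06 / 1.5 = 0.04; m1 = 0.12; observed = (0.456 + 0.022) / 0.94 = 0.5085. With HAH unaffected at 0.600, the difference is 9.15 points and RR = 0.600 / 0.5085 = 1.180.

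| Attrition | q, control / HAH | 3-fold ratio in | Control % | HAH % | Difference | RR |
|---|---|---|---|---|---|---|
| 6% | any | neither arm | 50.00 | 60.00 | 10.00 | 1.200 |
| 6% | 25% / 20% | both arms | 50.85 | 60.91 | 10.06 | 1.198 |
| 6% | 25% / 20% | control only | 50.85 | 60.00 | 9.15 | 1.180 |
| 6% | 25% / 20% | HAH only | 50.00 | 60.91 | 10.91 | 1.218 |
| 6% | 10% / 6% | control only | 50.43 | 60.00 | 9.57 | 1.190 |
| 6% | 10% / 6% | HAH only | 50.00 | 60.34 | 10.34 | 1.207 |
| 6% | 5% / 3% | control only | 50.23 | 60.00 | 9.77 | 1.194 |
| 6% | 5% / 3% | HAH only | 50.00 | 60.18 | 10.18 | 1.204 |
| 15% | 25% / 20% | control only | 52.35 | 60.00 | 7.65 | 1.146 |
| 15% | 25% / 20% | HAH only | 50.00 | 62.52 | 12.52 | 1.250 |

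For scale, the standard error of the difference with 329 and 658 patients is √(0.25/329 + 0.24/658) = 3.4 points, so 0.85 points is about a quarter of it.

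**Does imputation help?** Simulation (1050 patients, 400 replicates, 20 imputations; q = 25% / 20%; 3-fold ratio in controls only), differences in points:

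| Missing | Full data | Complete case | MI without 1-month status | MI with 1-month status |
|---|---|---|---|---|
| 6% | 9.8 | 9.0 | 9.0 | 9.8 |
| 15% | 10.1 | 7.7 | 7.7 | 10.0 |

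The imputation without 1-month status used arm only. Baseline predictors that carry information about 1-month status would recover part of the gap, so the third column is a worst case.

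**The case against.** **The missing-at-random sentence is not false.** Likelihood inference is valid when missingness depends only on the model's covariates, and the SAP adds that the mechanism will be explored. This stands: the fault is that the wording misleads, not that the model has no validity under missing at random.

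**Bias is not shown.** A reader might infer that both analyses are biased. The documents do not support that. Loss must depend on 1-month status beyond the model covariates and, for the relative risk, do so differently by arm. No figure in the SAP points to such a difference, and its direction is unknown.

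**Large effects need extreme inputs.** A bias of 2.5 points at 6% attrition takes 40% against 0% missingness by 1-month status. Recorded deaths are coded 0, section 2.1.1 counts inpatients with no record of residential care as at home, and section 2.1.2 has the trial manager ask the site about death when both forms are absent. The share at risk is therefore mainly living patients in residential care. With 5% to 10% of controls in that state, 20% against 3.5% missing and 20% of them later at home, the control rate shifts by only about 0.3 to 0.5 points.

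**The visit-date condition.** Section 2.1.1 gives a 1 only if a visit date exists, so a reader might infer that patients imputed as at home stay missing while imputed failures count. With 12% of controls and 3% of HAH patients missing, that would give 154/329 = 46.8% against 407.4/687.4 = 59.3%, or 12.5 points. Those loss rates are assumed, and on the same reading sensitivity analysis 2(i) would do nothing for such patients, which cannot be intended. It is an ambiguity to close, not a demonstrated error.

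**Other sensitivity analyses exist.** Item 1 adds baseline factors only. Item 2 departs from missing at random but gives all missing patients the same state in both arms. Item 4 comes later and adds 12-month, not 1-month, outcomes. None replaces an imputation that uses early status.

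**Practice may be a slip for centre, and 1-month home status is uncertain.** Both are fair. Appendix II has one combined row, and the outcome is defined only at 6 and 12 months. Residential care and hospital admission at 1 month are clearly collected.

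**Conclusion.** The point holds in limited form. The primary analysis is complete-case, section 4.2 describes it misleadingly, and the imputation cannot check loss related to early deterioration because it lists only baseline variables and omits IQCODE.

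The possible shared bias is about 1 percentage point or less at 6% attrition with a 3-fold ratio in one arm, in either direction (RR 1.18 to 1.22 against 1.20). It is about 2.4 to 2.5 points at 15% attrition under the same assumptions. If the dependence is equal in both arms at 6% attrition, the relative risk hardly moves (1.198). The shares at 1 month, the later home rates and the missingness ratio are all assumptions. The change is worth making because it costs almost nothing and gives the imputation a purpose that the other sensitivity analyses do not serve.

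**What to change.** Section 4.2: replace the sentence on data missing at random with a statement that the primary analysis is complete-case and assumes that missingness depends only on arm, gender, IQCODE and centre.

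Section 6 item 3:

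- Impute the binary living-at-home outcome directly, so that the visit-date condition in section 2.1.1 cannot drop patients imputed as at home.
- Include every analysis-model variable: arm, gender, IQCODE, and centre in place of practice.
- Add 1-month residential-care and hospital-admission status and, where recorded, living-at-home status, with their relation to the outcome allowed to differ by arm.

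Cost: SAP wording and a longer imputation model, with no new data collection.

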4.3 HANDLING OUTLIERS

Any outliers will be checked and verified to ensure that they are true values. No statistical analysis will be conducted to assess the impact of potential outliers on the results.

4.4 MULTIPLE COMPARISONS AND MULTIPLICITY

The primary outcome is clearly stated in the protocol and no adjustment for multiple comparisons will be made.

4.5 MODEL ASSUMPTIONS

Model assumptions will be assessed using graphical representation of residuals. If the assumptions for the primary analysis are not satisfied, a non-parametric test, such as a chi-squared test or Fisher's Exact Test will be used.

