2.3 SAMPLE SIZE

The sample size is calculated for the primary outcome: living at home at 6 months follow up (the inverse of death or living in a residential care setting), for a 2:1 randomisation ratio with 2/3rd randomized to admission avoidance HAH with CGA and 1/3 to inpatient CGA. Several sources informed our estimate of effect size; these were one of the trials included in the IPD meta-analysis of HAH which recruited frail older people who required hospital level care (similar to the study population we plan to recruit), an audit of 750 patients who received HAH + CGA in Lanarkshire, the RCTs of CGA included in the Cochrane Review and the pooled estimate for the relative effect at 6 months obtained from the IPD Cochrane Review of HAH (3 trials, 607 participants) which was an adjusted Hazard Risk of 0.62 (95% CI 0.45 to 0.87) for mortality. Our proposed study effect estimate is based on a control group (CGA hospital) event rate at 12 months of 50% with a 10% reduction in living in a residential setting to 40% in the CGA at home group, equal to a relative risk of 0.8 which lies towards the top end of the 95% CI for the pooled estimate. We have calculated that a sample size of 1050 to achieve around 83% power at a significance level of 0.05 to detect a 10% absolute difference, assuming a control group event rate at 12 months of 50% and 6% attrition.

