3.4 POOLING OF INVESTIGATIONAL SITES

Analysis will not be pooled as the primary and secondary analysis sufficiently account for the different centres.

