Activities of daily living is measured at baseline and 6 months by the Barthel index and is a continuous variable. A linear mixed effects model will be fitted to the data with activities of daily living at 6 months as the dependent variable. The model will include intervention arm, baseline Barthel index score, gender, and know cognitive decline (IQCODE) as fixed effects, as well as centre as a random effect. The intervention effect with 95% confidence intervals and p value for activities of daily living at 6 months will be estimated from the model.

7) Readmission or transfer to hospital at 1 month and 6 months

Readmission or transfer at 1 month and 6 months (*hadmityn*) is a binary variable (0 = No, 1 = Yes). A generalised linear mixed model will be fitted to the data with readmission or transfer to hospital at 1

and 6 months as the dependent variable. The model will include intervention arm, gender, and known cognitive decline as fixed effects, and centre as a random effect. The model will also include a random intercept for each patient. The adjusted relative risk with 95% CI and p-values for activities of daily living at 1 month and 6 months will be estimated from the model.

The distribution of the models will be assessed and the assumptions of the models will be checked. If any of the assumptions are violated the first option would be to apply a suitable transformation to the data, if this is not possible then a non-parametric test will be applied to the data (i.e. chi-Squared test). If a non-parametric test is adopted, it will not be possible to adjust for covariates.

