11 CHANGES TO THE PROTOCOL OR PREVIOUS VERSIONS OF SAP

The primary outcome in the published protocol was originally planned to include data collected at both the 6 and 12 months' time point. However, it was decided to analyse the data collected at the two time points separately because it is now planned to potentially publish the results from the 6 months analysis before the 12 month follow-up is complete. All data that is collected at the 12 months' time point will be analysed separately from the 6 months data. In terms of the primary outcome, the analysis of both the 6 and 12 month data will be conducted as a sensitivity analysis.

The statistical analysis methods section in the published protocol states that the primary outcome of 'living at home' and other binary outcomes will be analysed using a mixed-effect logistic regression model. It has been decided to analyse the binary outcome by means of a generalised linear mixed model instead so that relative risk measures can be obtained from the model.

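### Section 4.5 lets an undefined residual-plot check swap the adjusted primary model for a chi-squared or Fisher's test, which cannot give the planned adjusted relative risk

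*SAP*

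**What the plan says.** - **Section 2.1.1** defines the primary outcome, living at home at 6 months, as a 0/1 variable.
- **Section 4.1** fits a generalised linear mixed model with arm, gender and the full IQCODE score as fixed effects and centre as a random effect. From it come an adjusted relative risk, 95% CI and p-value. No distribution or link is named.
- **Section 11** explains why this model replaced the protocol's mixed logistic regression: "so that relative risk measures can be obtained from the model".
- **Section 4.5** sets the check and the consequence: "Model assumptions will be assessed using graphical representation of residuals", and then "If the assumptions for the primary analysis are not satisfied, a non-parametric test, such as a chi-squared test" or Fisher's exact test.
- **Section 5.1**, closing paragraph, has a similar rule for all secondary models: "the first option would be to apply a suitable transformation to the data", then a non-parametric test, with chi-squared as the only one named. It concedes that covariate adjustment is then lost.
- **Section 4.1** also handles small centres: "If sites recruited only a small number of patients to the study then these will be grouped together". Section 3.4 says: "Analysis will not be pooled as the primary and secondary analysis sufficiently account for the different centres".

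**The concern.** A fallback for a primary analysis should have a trigger that two statisticians would apply in the same way, and it should still answer the question the trial asked. Section 4.5 does neither.

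The trigger is a visual judgement made on outcome data, with no residual type and no criterion. The replacement is a different analysis: a p-value from a two-by-two table, without the stratification factors and without the adjusted relative risk and interval. If the rule were used, the headline result would no longer be the one section 4.1 specifies, and a reader could not tell whether the switch was forced or chosen.

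It is also not a remedy. A chi-squared test repairs no fault that a residual plot might show in the mixed model; it simply ignores centre and covariates.

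**Working it through.** **1. The design figure, reproduced.** Inputs from section 2.3: "We have calculated that a sample size of 1050 to achieve around 83% power at a significance level of 0.05"; "assuming a control group event rate at 12 months of 50% and 6% attrition"; 40% in the intervention arm; 2:1 allocation. A two-sided test is assumed, since sidedness is not stated.

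- Pooled proportion: (0.5 + 2 × 0.4)/3 = 0.4333.
- Control patients for 83% power: [1.960 × √(0.4333 × 0.5667 × 1.5) + 0.954 × √(0.25 + 0.24/2)]² / 0.1² = (1.1895 + 0.5804)² / 0.01 = 313.3, so 314.
- With continuity correction: 314/4 × [1 + √(1 + 6/(2 × 314 × 0.1))]² = 328.8, so 329 control + 658 intervention = 987.
- With 6% attrition: 987/0.94 = 1050, as stated.
- Power at 987: z = (0.1 − 1.960 × 0.03346)/0.03354 = 1.026, or 84.8%. With continuity correction (subtract 0.00228 from the difference) z = 0.958, or 83.1%.

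No design figure is wrong. The match also suggests that the trial was powered on an unadjusted comparison of two proportions, which matters when judging the fallback's power.

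**2. What is promised and what the fallback delivers.**

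| | Section 4.1 model | Section 4.5 fallback |
|---|---|---|
| Effect measure | adjusted relative risk | none from the test |
| 95% CI | yes | none from the test |
| Gender, IQCODE | fixed effects | dropped |
| Centre | random effect | dropped |
| Trigger | – | residual plots, no criterion |

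Section 2.4 stratifies randomisation by centre, gender and known cognitive decline, so the fallback drops every stratification factor.

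**3. Why raw residual plots are a weak trigger.** The raw residual is y − p̂, so it equals 1 − p̂ or −p̂. At p̂ = 0.6 it is 0.4 or −0.6; at p̂ = 0.5 it is 0.5 or −0.5. The plot shows two bands however good the fit.

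**4. The failure without a rule.** If a log link is used to obtain relative risks, covariate and centre effects multiply the probability. The section 2.3 event rates of 40% and 50% imply 60% and 50% at home. A patient whose combined effects exceed 1/0.6 = 1.67 (intervention) or 1/0.5 = 2 (control) then has a fitted probability above 1. Those rates are described as 12-month rates; a higher proportion at home at 6 months would leave less room. With a continuous IQCODE in the model, out-of-range fits or non-convergence are foreseeable.

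**5. Size of the loss.** This simulation is illustrative, and its effects are assumed, not taken from the SAP. It used 987 patients, 10 centres, centre SD 0.4, gender effect 0.3, IQCODE effect 0.8 per SD and treatment effect 0.47 under the alternative (all on the logit scale). Randomisation was 2:1 in blocks of three within strata, with 2,000 runs per scenario. The adjusted comparator was logistic regression with fixed centre effects, standing in for the mixed model.

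| Analysis | Type I error | Power |
|---|---|---|
| Chi-squared, uncorrected | 3.7% | 84.6% |
| Chi-squared, corrected | 3.1% | 83.2% |
| Fisher's exact | 3.3% | 83.9% |
| Covariate-adjusted | 5.1% | 88.2% |

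The loss is 88.2 − 84.6 = 3.6 to 88.2 − 83.2 = 5.0 points. Two other simulations, under different assumptions, compared chi-squared with robust Poisson and gave 84 − 81 = 3 points (300 runs) and 87 − 85 = 2 points. In the 300-run simulation each figure has a Monte Carlo standard error of about 2 points (√(0.81 × 0.19/300) = 0.023).

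**6. Secondary outcomes.** Transformation is a reasonable option for the continuous Barthel score but cannot change a 0/1 outcome. A chi-squared test does not suit the Barthel score. Nor does it suit delirium, residential care or readmission, which section 5.1 models as repeated measures with a random intercept for each patient.

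**The case against.** The best defence is that the fallback is safe. It appears to be the comparison the trial was powered on, it keeps about the planned 83% power, and it is conservative. It may never be used. Two bands are a feature of raw residuals only; binned or simulated residuals and plots of centre effects are also graphical checks, and section 4.5 does not exclude them. All of this stands, and it limits the point to the estimand and pre-specification. It does not supply a criterion or restore the adjusted relative risk.

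Some stronger readings are tempting but not supported:

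- *Power could fall to about 50%.* That figure applies to a Poisson model with model-based errors. The SAP never mentions Poisson, so this would be a consequence of an unstated choice, not of section 4.5.
- *The relative-risk model will nearly always fail.* Simulated log-binomial failure rates ranged from 40% to 99% depending on the assumed IQCODE effect, with default starting values. They show that the risk is real, not how large it is in this trial.
- *Sections 3.4 and 4.1 contradict each other on pooling.* Section 3.4 reads naturally as saying that centre will not be ignored, and a random effect with a merged level still models centre. What remains is that a small number of patients is not defined.
- *The switch would be made after unblinding.* Section 2.4 covers participants and research nurses only. The SAP does not say when the check is made or whether the analyst then knows the allocation.

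**Conclusion.** The point holds for section 4.5 as written. An uncriterioned look at residual plots can replace the primary adjusted relative risk and CI with an unadjusted test that drops all stratification factors, contrary to section 4.1 and to the purpose stated in section 11. The foreseeable problem, non-convergence or fitted probabilities above 1, is left without a rule.

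The cost in operating characteristics is modest: type I error about 3–4% and roughly 3–5 points of power. It rests on assumed covariate and centre effects and would shrink if those effects were weaker. The simulations apply each test throughout; they do not model a choice between tests made after seeing results. A reader should not infer inflated type I error from the fallback itself, or a wrong sample size. The change should be made because it is cheap and governs the primary result.

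**What to change.** 1. **Section 4.1:** name the distribution and link of the primary model.
2. **Section 4.5:** delete the chi-squared/Fisher fallback. Pre-specify that, if the model does not converge or gives fitted probabilities of 1 or more, the adjusted relative risk and 95% CI come from a Poisson log-link model with robust (sandwich) variance, or from a logistic model with standardised relative risk. Choose one of the two now. Keep the same covariates and account for centre.
3. **Section 5.1:** apply the same rule to the other binary outcomes, and remove the chi-squared fallback for the repeated ones and for Barthel. Limit transformation to the Barthel score, with bootstrap CIs if its residuals are poor.
4. **Minor, section 4.1:** fix the threshold for merging small sites before the data are seen, or do not merge under the random-effect model, which already shrinks small centres. That argument does not carry over to a fallback with fixed centre terms, where sparse centres can be a real problem; if that form is chosen, state how they are handled.

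The cost is SAP wording and slightly more programming. Sample size and data collection do not change.
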